[figure not shown]

Statistical/Programming Plan for Cue Reward Trial Analysis

Protocol Version Date: 2022-12-16

- 1. Title:** Medication Adherence Patterns in Rheumatic Diseases: A Behavioral Trial: Phase 2 trial results
- 2. Core research team**
PI: [name]; Co-PI: [name]
- 3. Aim(s): To determine whether strategies that couple context cues and rewards improve adherence to medications**
- 4. Data source:**
 - a) REDCap data for 56 consented patients (20 = in Adaptive intervention; 18 = in Non-Adaptive Intervention; 18 = in Control) – one dataset
 - b) Pillsy pill bottle adherence data for 56 patients - there are N= 352 daily 000_Pillsy files spanning the length of the trial
 - c) IRB: 2020P003826
 - d) NIA (NIH) funded P30

5. Overall trial diagram:

6. Cohort Identification

6.1 Cohort Summary

There will be 1 cohort formed at the **patient level**.

Each patient should already be identified with the following in the REDCap dataset:

- e) Patient Study ID (i.e., Record_id)
- f) Arm (arm) (0 = Control, 1 = Non-adaptive intervention, 2 = Adaptive intervention)

6.2 Important steps for cohort formation

6.2.1 Eligible study entry dates/definitions and the corresponding variable names in REDCap.

- a) **Screening date:** Date each patient was screened for eligibility for the study and began being contacted for enrollment. (mail_date)
- b) **Enrollment date:** Date each patient was enrolled and consented into the study. (date_consent)
- c) **Index date:** Each patient began receiving the intervention (either of the text messaging interventions or control). (start_date)
- d) **Intervention Completion date:** Index date (inclusive) to 12 weeks beginning on the index date (intervention_date)
- e) **Follow-up period:** Index date (inclusive) to 18 weeks beginning on the index date for primary adherence and secondary outcomes.

6.2.2 Specify inclusion criteria for cohort entry and define the index date

Patients are already identified by their study ID (56 patients altogether). The index date is the first day of intervention (“start_date” in REDCap).

7. Variables

7.1 Exposure-related variables:

Patient-level cohort: Within this cohort, please measure and provide the following variables at the patient level:

a) Using the **REDCap file:**

- Patient demographics:
 - Age (age_years, age), numeric. Please also calculate using dob and start_date
 - Sex (sex)
 - 0 = Not listed
 - 1 = Female
 - 2 = Male
 - Sex if Sex is not listed (sex_other)
 - Race/ethnicity (self reported)
 - 1 = White
 - 2 = Black or African American
 - 3 = American Indian/ Alaska Native
 - 4 = Asian
 - 5 = Native Hawaiian or Other Pacific Islander
 - 6 = Hispanic/Latinx
 - Education level (education)
 - 1 = Less than high school diploma
 - 2 = High school diploma
 - 3 = Some college
 - 4 = College degree
 - 5 = Graduate degree
 - Marital status (marital)
 - 1 = Married
 - 2 = Living with partner/ Domestic partnership
 - 3 = Widowed
 - 4 = Divorced/ Separated
 - 5 = Never married/ Single
 - Employment Status (employment)
 - 1 = Employed
 - 2 = Job seeking

- 3 = Not job seeking
- 4 = Retired
- 5 = Disabled
- Income (self-reported) (income)
 - 1 = Less than \$20,000
 - 2 = \$20,000 to \$34,999
 - 3 = \$35,000 to \$49,999
 - 4 = \$50,000 to \$74,999
 - 5 = \$75,000 to \$99,999
 - 6 = Over \$100,000
 - 7 = Prefer not to say
- Number of self-reported medications on a daily basis (num_meds_daily)
- Number of self-reported medications on a weekly basis (num_meds_weekly)
- Recruitment method (rec_type)
 - 1 = PCP
 - 2 = Rheumatology
- Baseline Uric acid (ua_baseline) used for the study, numeric
- Baseline Uric acid date (ua_baseline_date)
- Baseline Uric acid stratum (ua_stratum)
 - 1 = 6-8 mg/dl
 - 2 = >8 mg/dl
- Arm (arm):
 - 0 = Control,
 - 1 = Non-adaptive intervention,
 - 2 = Adaptive intervention
- Number of prescribed study medications (bottles), numeric
- Medication names (bottle_1_med, bottle_2_med, bottle_3_med)

7.2 Baseline Medication Use Questionnaire:

- 3-item questionnaire: Please perform a linear transformation of the following three variables to a scale of 100 and take the mean of the three for each patient, for those with baseline survey data:
 - missed_doses: numerical value, 0-30. For each day missed, calculate the percentage of days taken out of 30 (e.g. missed_doses=2 → 28/30 = 93.33)
 - medication_supposed :
 - 1=Never → 0
 - 2=Rarely → 20
 - 3=Sometimes → 40
 - 4=Usually → 60
 - 5=Almost Always → 80
 - 6=Always → 100
 - meds_good_job:
 - 1=Very Poor → 0
 - 2=Poor → 20
 - 3=Fair → 40

- 4=Good → 60
- 5=Very Good → 80
- 6=Excellent → 100
- Please generate a flag for missing any one of these fields (missed_doses, medication_supposed, meds_good_job)
- Automaticity score categories (automaticity): Present the scores for the 4 questions – automaticity_1_end to automaticity_4_end.
 - 0=No
 - 1=Yes
- Routine related questionnaire
 - Score the following from 1 (Not at all) to 7 (Very much so): routine, same_time, continue_way, take_same_place, take_right_before, take_water, take_same_cup, keep_same_place
- Perception related questionnaire
 - Score from 1 (Strongly Disagree) to 5 (Strongly Agree) the following: regular_apts, tx_plan_difference, med_help_control, prescribed_take_daily, not_taking_effect, feel_well_stop, live_long, control_gout, gout_better_worse, actions_effect

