1. Aggregate adherence (adh_daily) into the mean daily adherence value for each patient (ranging from 0 to 1) for the **18 weeks** from “start_date” to the end of follow up (if date range is less than 18 weeks, calculate just for the respective date range) → label this as “adherence_primary_outcome”
2. Repeat the aggregation of adherence for each patient omitting the first 7 days of data (i.e., index date → index date+7)
3. Repeat the aggregation of adherence for each patient omitting the first 14 days of data (i.e., index date → index date+14)
4. Repeat the aggregation of adherence for each patient, but censor patients in the adherence calculation at the time they have stopped using the electronic pill bottle for >30 days (defined as “adh_daily”=0 for >30 consecutive days in Pillsy data)
 - Please generate a flag for the patient (1/0) and provide the date in which they were censored if this occurs (leave the date as missing if does not occur)
5. Repeat the aggregation of adherence for each patient for the **12 weeks** from “start date” to the “intervention_date” (the intervention completion date) or “withdraw_date”, whichever is earlier.
6. Repeat the aggregation of adherence (adh_daily_allopurinolqd) for 18 weeks from “start_date” to the end of follow up for Allopurinol QD – label as “adh_allopurinol”.

d) Use generalized linear models (proc genmod) to compare nonadaptive vs. control and adaptive vs. control; calculate unadjusted mean differences for these groups and adjusted mean differences (adjusted for age, sex, race/ethnicity). The link=identity and dist=normal). Recruitment type (PCP vs. rheumatology) also accounted for in the model.

B) Uric acid level outcomes (Change in uric acid levels – Exploratory outcome)

a) Using the **REDCap file**:

- Please measure the difference between “ua_end” (outcome) and “ua_baseline” (baseline).
- Please provide the dates for both “ua_date_end” and “ua_baseline_date”
- Please provide a flag if missing “ua_end” (outcome)

b) Use generalized linear models (proc genmod) to compare nonadaptive vs. control and

adaptive vs. control; calculate unadjusted mean differences for these groups and adjusted mean differences (adjusted for age, sex, race/ethnicity). The link=identity and dist=normal). Recruitment type (PCP vs. rheumatology) and baseline uric acid level also accounted for in the model.

C) Self-Reported Outcomes:

- Automaticity scores (automaticity): automaticity_1_end to automaticity_4_end.
 - 0=No
 - 1=Yes

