- Routine related questionnaire
 - Score the following from 1 to 7: routine_end, same_time_end, continue_way_end, take_same_place_end, take_right_before_end, take_water_end, take_same_cup_end, keep_same_place_end
- Perception related questionnaire
 - Score from 1 (Strongly Disagree) to 5 (Strongly Agree) the following: regular_apts_end, tx_plan_difference_end, med_help_control_end, prescribed_take_daily_end, not_taking_effect_end, feel_well_stop_end, live_long_end, control_gout_end, gout_better_worse_end, actions_effect_end

D) Feasibility Outcomes:

- Score from 1 (Strongly **agree**) to 5 (Strongly **disagree**) the following: cue_useful, cue_text_useful, reward_text_useful

Requested Results:

Table 1: Baseline characteristics

	Usual Care	Non-adaptive	Adaptive
N, (%)			
Age (Mean, SD) (Median, IQR)			
Female (N, %)			
Partnered/ Marital status Married Living with partner/ Domestic partnership Widowed Divorced/ Separated Never married/ Single			

Race White Black or African American American Indian/ Alaska Native Asian Native Hawaiian or Other Pacific Islander Hispanic/Latinx			
Education level Less than high school diploma High school diploma Some college College degree Graduate degree			
Employment Employed Job seeking Not job seeking Retired Disabled			
Baseline Uric acid (mg/dL)			
Medication Use Baseline Automaticity score (Mean, SD) Routine Perception			
Recruitment method Rheumatology (N, %) PCP (N, %)			
Self-reported medications on a daily basis (Mean, SD)			
Self-reported medications on a weekly basis (Mean, SD)			
Number of prescribed study medications (N, %) 1 2 3			
Baseline self-reported adherence (Mean, SD)			
Disease activity (Mean, SD)			
Number of Pillsy bottles used in the study			

1 2+			
Patients intensified (adaptive arm)			

Table 2: Primary and Secondary Outcomes

	Control Mean (SD)	Non-adaptive intervention Mean (SD)	Adaptive intervention Mean (SD)	Unadjusted absolute difference	Adjusted absolute difference		
				(Non-adaptive vs Control)	(Adaptive vs Control)	(Non-adaptive vs Control)	(Adaptive vs Control)
Primary Outcome:							
Adherence							
Secondary Outcome:							
Change in uric acid levels							
Change in automaticity							
Change in perception							
Change in sense of routine

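### SAP section 7.2 names the end-of-study automaticity fields as the baseline fields, so the change in automaticity is zero by construction and the Table 1 row holds post-randomisation answers

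*SAP*

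**What the plan says.** SAP section 7.2 is headed "Baseline Medication Use Questionnaire". For automaticity it instructs: "Present the scores for the 4 questions – automaticity_1_end to automaticity_4_end", each item coded 0 for no and 1 for yes. Section 8.C, which lists the self-reported outcomes, reads: "Automaticity scores (automaticity): automaticity_1_end to automaticity_4_end", with the same coding. Both entries carry the same label, `automaticity`.

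Two tables draw on these fields:
- Table 1, the baseline characteristics table, contains "Baseline Automaticity score (Mean, SD".
- Table 2 lists "Change in automaticity" under its secondary outcome heading. It has columns for the three arm means and for the unadjusted and adjusted differences of each intervention arm from control.

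The other measures are named differently at the two times. For routine, section 7.2 has "Score the following from 1 (Not at all) to 7 (Very much so): routine, same_time, continue_way" and section 8.C has "Score the following from 1 to 7: routine_end, same_time_end, continue_way_end". For uric acid, section 8.B writes the change out: "Please measure the difference between “ua_end” (outcome) and “ua_baseline” (baseline".

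**The concern.** The SAP is a programming plan that identifies its data by REDCap variable name, so a wrong name is a wrong instruction. Here the baseline and outcome sections point to one set of fields, and that set carries the suffix the SAP otherwise keeps for follow-up.

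Two results are at stake. The change in automaticity could not show a difference between arms, whatever happened in the trial. The baseline table would contain end-of-study answers, so an effect of the intervention on automaticity would look like a baseline imbalance. The first error would probably be noticed, because a row of zeros is conspicuous. The second is harder to see, because 0/1 answers from the end survey look like plausible baseline answers.

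Automaticity also matters to this trial in particular. The protocol's background section describes habit as an automated response, and the trial tests a habit-formation model.

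**Working it through.** The plan gives no figure to reproduce on this point. The check compares the field lists and then follows the instruction through to the tables.

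**1. Field names at the two times (SAP 7.1, 7.2, 8.B and 8.C)**

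| Measure | Baseline name | End name | Distinct names |
|---|---|---|---|
| Routine | no suffix | `_end` | 8 of 8 |
| Perception | no suffix | `_end` | 10 of 10 |
| Uric acid | `ua_baseline` | `ua_end` | 1 of 1 |
| Automaticity | `automaticity_1_end` to `automaticity_4_end` | `automaticity_1_end` to `automaticity_4_end` | 0 of 4 |

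Outside automaticity, 8 + 10 + 1 = 19 of 19 measures have distinct names, and the end-labelled one is always the follow-up value. The protocol (Subject Selection) also places a participant survey at the end of the study period, after randomisation.

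**2. Change score**

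Let f be any rule that turns the four 0/1 items into a score. The SAP writes a change formula only for uric acid, as a difference between the end and baseline values. With that pattern:

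change = f(fields in 8.C) − f(fields in 7.2) = f(`_end` items) − f(`_end` items) = 0.

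This holds for any f. It was confirmed for all 2⁴ = 16 answer patterns under four rules (sum, mean, any, all): the only value obtained was 0. For a patient without end answers, the result is missing.

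**3. Table 2**

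The row has 3 arm means + 2 unadjusted differences + 2 adjusted differences = 7 cells. Each arm with data has mean 0 and SD 0. Both contrasts with control are 0, with no residual variance from which to estimate a standard error. This is 1 of the 4 rows under the secondary heading (uric acid, automaticity, perception, routine).

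**4. Patients affected**

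The SAP has 18 control + 18 non-adaptive + 20 adaptive = 56 patients. If n of them answered the end survey, change is 0 for n and missing for 56 − n. The documents do not give n, so it can only be placed between 0 and 56. The result is uninformative for every n in that range.

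**5. Table 1**

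The 3 arm cells of the automaticity row are filled from the `_end` items, which are post-randomisation answers.

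**6. With distinct baseline fields**

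If the four items are summed to a 0–4 score, the change can take any whole value from −4 to +4, and the Table 2 row can be estimated. Its actual value cannot be derived from the documents.

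**The case against.** The strongest objection is that the SAP never orders this subtraction. It gives no change formula for automaticity: section 7.2 only asks for the scores to be presented, and 8.C only lists fields. On the strictest reading the change is undefined rather than zero. That is correct, and the zero depends on the ordinary meaning of change, which the SAP spells out only for uric acid. It does not rescue the row, because an undefined change cannot be reported either.

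A second objection is that the slip nearly corrects itself. The consistent naming elsewhere would lead a careful programmer to look for unsuffixed fields, and anyone puzzled by zeros in Table 2 would trace them to the field list and so to Table 1. This may well happen. But the SAP does not name such fields and the documents do not show that they exist, so the written instruction remains wrong.

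Third, the Table 1 cell text is run together in the extracted document, and the word Baseline may belong to the preceding line. The table is still the baseline characteristics table, so the row is a baseline row either way.

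Fourth, the consequence is limited. This is a pilot, the Table 1 row enters no model stated in the SAP, and the status of the secondary outcomes is itself unsettled: section 8.B calls uric acid exploratory, while Table 2 lists it as secondary. These points limit the weight of the finding but do not remove the error.

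**Conclusion.** The concern holds. As written, the SAP has no baseline measure of automaticity. Followed literally, all 7 cells of one of four secondary rows in Table 2 carry no information, and 3 cells of one descriptive row in Table 1 hold post-randomisation answers.

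The conclusion rests on two readings: that change means end minus baseline, and that `_end` has the same meaning for automaticity as it has for the other measures. The most likely cause is text copied from section 8.C. The documents do not show which fields the executed program used, so this is a finding about the plan and not about the reported results. The primary adherence outcome and the uric acid, routine and perception rows are not affected. The error should be corrected, but it does not threaten the trial's main conclusion.

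**What to change.** - In section 7.2, replace the four `_end` fields with the baseline survey fields, confirmed against the REDCap dictionary. The documents do not give their names.
- Give the baseline and end scores different labels, since both are now called `automaticity`.
- State how the four 0/1 items form the score. Table 1 asks for a mean and SD, and section 7.2 gives no rule.
- Define change in automaticity as end minus baseline.
- For the adjusted difference, keep the change score as the outcome and add the baseline score as a covariate, as the uric acid model in section 8.B does with baseline uric acid. The SAP states no model for the self-reported outcomes, so this follows the plan's own precedent.
- If baseline automaticity was not collected, remove the Table 1 row and replace the Table 2 change row with a between-arm comparison of the end-of-study score.
- Check the executed program to see which fields it read.

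The field correction costs one or two lines of SAP text and one look at the REDCap dictionary. No new data are needed if the baseline items were collected.

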7.3 Baseline Gout Questionnaire

- gout_1 (1 = Yes, 0 = No)
- gout_2 (1 = Yes, 0 = No)
- gout_3 (1 = Yes, 0 = No)
- gout_4 (Score from 1 to 10)

8. Outcome variables and study follow-up:

A) Primary Outcome (Average daily adherence):

For each patient, please measure the following outcomes beginning on the index date:

- a) Follow-up period for each patient
 1. Some patients may not have a full 18 weeks of follow-up. This is based on the time between the index date (start_date) and the end date (study_date) or (withdraw_date) whichever is earlier in REDCap. Please provide the number of days between the index date and the end date in REDCap.
- b) Calculate daily adherence during the follow-up period (adh_daily), using the available time stamps from the 352 daily **Pillsy files** merged with the **REDCap file**:
 1. Daily adherence values are calculated from Pillsy files, while date information should be taken from REDCap file.
 2. Medications are named using “Medication # QD/BID” (drugName). If name includes “QD”, count as 1 expected daily dose; if name includes “BID”, count as 2 expected daily doses.
 3. Time stamps (eventTime) within 3 hours of each other (e.g. 9:00am and 11:59am) should be collapsed into one dose. There will likely be multiple time stamps for each opening, but they should be counted as one dose.
 4. Time stamps between 12:00am and 3:00am should be counted as taken on the previous calendar date (i.e., the day before).

5. Adherence is calculated as taking all expected doses of medications, with each medication weighted equally.
 - E.g., If a patient has 1 QD med and 2 BID meds, their calculation would be $(1/3)(X/1) + (1/3)(X/2) + (1/3)(X/2) = 1$
6. Please provide the calculated daily adherence values for all the patients as a separate dataset containing the record_id and the calculated daily adherence values.
7. Separately, please also provide the daily adherence for Allopurinol QD only. This variable will later be used for sensitivity analysis. The daily adherence will be recorded as a binary variable (1/0) – (adh_daily_allopurinolqd)
 - E.g., if a patient takes 1 QD Allopurinol, their adherence for that day would be either 1 or 0.

c) Using these daily calculations, generate the following adherence measure outcomes:

1. Aggregate adherence (adh_daily) into the mean daily adherence value for each patient (ranging from 0 to 1) for the **18 weeks** from “start_date” to the end of follow up (if date range is less than 18 weeks, calculate just for the respective date range) → label this as “adherence_primary_outcome”
2. Repeat the aggregation of adherence for each patient omitting the first 7 days of data (i.e., index date → index date+7)
3. Repeat the aggregation of adherence for each patient omitting the first 14 days of data (i.e., index date → index date+14)
4. Repeat the aggregation of adherence for each patient, but censor patients in the adherence calculation at the time they have stopped using the electronic pill bottle for >30 days (defined as “adh_daily”=0 for >30 consecutive days in Pillsy data)
 - Please generate a flag for the patient (1/0) and provide the date in which they were censored if this occurs (leave the date as missing if does not occur)
5. Repeat the aggregation of adherence for each patient for the **12 weeks** from “start date” to the “intervention_date” (the intervention completion date) or “withdraw_date”, whichever is earlier.
6. Repeat the aggregation of adherence (adh_daily_allopurinolqd) for 18 weeks from “start_date” to the end of follow up for Allopurinol QD – label as “adh_allopurinol”.

d) Use generalized linear models (proc genmod) to compare nonadaptive vs. control and adaptive vs. control; calculate unadjusted mean differences for these groups and adjusted mean differences (adjusted for age, sex, race/ethnicity). The link=identity and dist=normal). Recruitment type (PCP vs. rheumatology) also accounted for in the model.

B) Uric acid level outcomes (Change in uric acid levels – Exploratory outcome)

a) Using the **REDCap file**:

- Please measure the difference between “ua_end” (outcome) and “ua_baseline” (baseline).
- Please provide the dates for both “ua_date_end” and “ua_baseline_date”
- Please provide a flag if missing “ua_end” (outcome)

b) Use generalized linear models (proc genmod) to compare nonadaptive vs. control and

adaptive vs. control; calculate unadjusted mean differences for these groups and adjusted mean differences (adjusted for age, sex, race/ethnicity). The link=identity and dist=normal). Recruitment type (PCP vs. rheumatology) and baseline uric acid level also accounted for in the model.

C) Self-Reported Outcomes:

- Automaticity scores (automaticity): automaticity_1_end to automaticity_4_end.
 - 0=No
 - 1=Yes
- Routine related questionnaire
 - Score the following from 1 to 7: routine_end, same_time_end, continue_way_end, take_same_place_end, take_right_before_end, take_water_end, take_same_cup_end, keep_same_place_end
- Perception related questionnaire
 - Score from 1 (Strongly Disagree) to 5 (Strongly Agree) the following: regular_apts_end, tx_plan_difference_end, med_help_control_end, prescribed_take_daily_end, not_taking_effect_end, feel_well_stop_end, live_long_end, control_gout_end, gout_better_worse_end, actions_effect_end

D) Feasibility Outcomes:

- Score from 1 (Strongly **agree**) to 5 (Strongly **disagree**) the following: cue_useful, cue_text_useful, reward_text_useful

Requested Results:

Table 1: Baseline characteristics

	Usual Care	Non-adaptive	Adaptive
N, (%)			
Age (Mean, SD) (Median, IQR)			
Female (N, %)			
Partnered/ Marital status Married Living with partner/ Domestic partnership Widowed Divorced/ Separated Never married/ Single			

Race White Black or African American American Indian/ Alaska Native Asian Native Hawaiian or Other Pacific Islander Hispanic/Latinx			
Education level Less than high school diploma High school diploma Some college College degree Graduate degree			
Employment Employed Job seeking Not job seeking Retired Disabled			
Baseline Uric acid (mg/dL)			
Medication Use Baseline Automaticity score (Mean, SD) Routine Perception			
Recruitment method Rheumatology (N, %) PCP (N, %)			
Self-reported medications on a daily basis (Mean, SD)			
Self-reported medications on a weekly basis (Mean, SD)			
Number of prescribed study medications (N, %) 1 2 3			
Baseline self-reported adherence (Mean, SD)			
Disease activity (Mean, SD)			
Number of Pillsy bottles used in the study			

1 2+			
Patients intensified (adaptive arm)			

Table 2: Primary and Secondary Outcomes

	Control Mean (SD)	Non-adaptive intervention Mean (SD)	Adaptive intervention Mean (SD)	Unadjusted absolute difference	Adjusted absolute difference		
				(Non-adaptive vs Control)	(Adaptive vs Control)	(Non-adaptive vs Control)	(Adaptive vs Control)
Primary Outcome:							
Adherence							
Secondary Outcome:							
Change in uric acid levels							
Change in automaticity							
Change in perception							
Change in sense of routine

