Participants will be asked to use the electronic pill bottle for 5 months. As participants receive medication refills, they will transfer their pills to the Pillsy electronic pill bottle. Throughout the study, participant medication use data will be captured by the electronic pill bottles. The Pillsy electronic pill bottles employ electronic date/time stamp technology that is triggered by opening the pill bottle. Dates and times of bottle opening (and therefore adherence) are transmitted by Bluetooth to the patient's phone through the Pillsy mobile application.

The mobile application data will be automatically transferred to a secure, password-protected Pillsy portal hosted on a secure server located outside of BWH. These uploaded data will be deidentified, except for bottle opening dates and times. Participants will be assigned a study-specific ID, and the electronic bottles will only be linked to this participant by the study-specific ID. These data will only be accessible to the Partners researchers with password-protected access to the Pillsy portal. The only potentially identifiable data in the Pillsy portal are bottle opening dates, times, and study-specific ID.

• Arm A: Non-adaptive intervention

Patients in the first intervention arm will participate in a goal-setting exercise during which they will identify which habit they want to link their medication-taking to (see Attachments). For example, a patient who takes their medication in the morning may elect to link tooth brushing with medication taking. If a patient is non-adherent, patients will receive a text message up to every 4 days reminding them of the habit they decided to link to their medication-taking (see Attachments).

Patients in the first intervention arm will also select a charity to which a donation will be made every time the bottle is opened. The research team will donate \$0.50 every day that the patient takes their medication as prescribed. Patients will pick between the charities below:

PI: [name]

Version 16. October 10, 2022

- Animal Rescue League of Boston
- UNICEF
- Greater Boston Area Food Bank

A research assistant will place a sticker with the charity logo under pill bottle cap so that the patient is reminded of the donation every time they take the medication (see Attachments). Additionally, the patient will receive texts every 4 days summarizing how much money was donated on their behalf.

• Arm B: Adaptive intervention

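### On its natural reading the SAP scores days whose bottle data were never recovered as missed doses, and the >30-day censoring cannot tell lost data from non-use; a scoring rule and a count of lost days by arm would be a cheap improvement

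*SAP*

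**What the plan says.** The primary outcome is each patient's mean daily adherence over 18 weeks from the index date. For the daily values, SAP 8.A.b asks the programmer to "Calculate daily adherence during the follow-up period (adh_daily), using the available time stamps from the 352 daily" Pillsy files, and item b.1 separates the two sources: "Daily adherence values are calculated from Pillsy files, while date information should be taken from REDCap file". The stamps come from bottles that, in the protocol's Trial Period section, "employ electronic date/time stamp technology that is triggered by opening the pill bottle". A day's score is doses seen over doses expected, with medications weighted equally (item b.5).

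On what can shorten the window, 8.A.a.1 says "This is based on the time between the index date (start_date) and the end date (study_date) or (withdraw_date) whichever is earlier in REDCap", and 8.A.c.1 adds "if date range is less than 18 weeks, calculate just for the respective date range". Neither mentions days without data. Item c.4 repeats the aggregation but censors patients who have "stopped using the electronic pill bottle for >30 days (defined as “adh_daily”=0 for >30 consecutive days in Pillsy data".

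The protocol (Trial Period) foresees two ways in which daily data can be unavailable. A bottle may lose its link to the phone application: texts may then go to patients in any arm after three days, and staff may call after more than two weeks and again at study end. Or there may be a Pillsy or REDCap system problem. The SAP asks for missing-data flags for the baseline questionnaire (7.2) and for end-of-study uric acid (8.B), but for none on the bottle data. Tables 1 and 2 have no row for lost days.

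**The concern.** A day with no recorded opening can mean that the drug was not taken or that the record was lost. The SAP has one code for both. If lost days count as 0, measured adherence falls. Equal loss in all arms shrinks a true difference; unequal loss creates a false difference against the arm that loses more.

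Unequal loss is plausible for disconnection. Disconnection texts may go to all arms and the calls are not limited by arm. But only the intervention arms receive donation summaries every 4 days and, when triggered, cue texts. The outage message, which asks patients to stay connected, goes only to those actively receiving intervention texts. Outages themselves are system-side and should affect all arms.

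As no lost days are reported, a reader of the planned tables could not see either effect.

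**Working it through.** **Which reading the SAP supports.** The SAP's own example, one QD and two BID drugs, reproduces: (1/3)(1/1) + (1/3)(2/2) + (1/3)(2/2) = 1. With no stamps the same formula gives (1/3)(0/1) + (1/3)(0/2) + (1/3)(0/2) = 0. Dates come from REDCap, and only study end or withdrawal shortens the window, so a day without stamps stays in the denominator at 0. The alternative, averaging only days that have a stamp, does not work. A patient with one QD drug would score 1 on every counted day, and no day could be 0, so c.4 could never fire.

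**Inputs.** From the SAP: 18 × 7 = 126 days; 56 patients (20, 18, 18); 352 daily files. Assumed, because the documents give no figures: true adherence, and every loss level below.

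**Equal loss**, true adherence 0.80 against 0.70, fraction L of days lost: 0.10 × (1 − L) = 0.095 at L = 0.05 and 0.090 at L = 0.10. A 10-point difference becomes 9.5 or 9.0 points.

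**Unequal loss**, 0.80 in both arms, mean between-arm gap of d lost days per patient: 0.80 × d/126 = 0.0063, 0.0190 and 0.0444 at d = 1, 3 and 7. These are false differences of 0.6, 1.9 and 4.4 points.

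**A 7-day outage, never recovered.** Assume one file per calendar day, even entry, full follow-up and adherence 0.80.
- Fraction of patients in follow-up on an average day: f = 126/352 = 0.358, or 56 × 0.358 ≈ 20 patients.
- Loss per affected patient: 0.80 × 7/126 = 0.0444.
- Fall in an arm mean: 0.0444 × 0.358 = 0.0159, about 1.6 points.
- SD of the chance difference in affected fraction, 18 against 18: √[(56/55) × 0.358 × 0.642 × 2/18] = 0.161.
- Effect on the between-arm difference: 0.161 × 0.0444 = 0.0072, about 0.7 points (1 SD).

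**One disconnected patient**, adherence 0.80, unrecovered gap of g days: score 0.80 × (126 − g)/126, and shift in an 18-patient arm mean 0.80 × g/126/18.

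| g (days) | Patient score | Arm mean shift (points) |
|---|---|---|
| 3 | 0.781 | 0.1 |
| 14 | 0.711 | 0.5 |
| 28 | 0.622 | 1.0 |

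Three days is the protocol's threshold for a text. The 14- and 28-day gaps are illustrations only; the first staff call comes after more than two weeks.

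**What c.4 catches.** It needs 31 consecutive zeros. Take a once-daily patient at 0.80 with independent days, so a miss probability of 0.2 per day on each side of an interior gap.
- 30-day gap, at least 1 adjacent miss needed: 1 − 0.8² = 0.36.
- 28-day gap, at least 3 adjacent misses needed: 1 − 0.64 × (1 + 2 × 0.2 + 3 × 0.04) = 0.027.
- 31-day gap on days 31–61: c.4 fires whatever the cause and drops 126 − 61 = 65 later days, even if they were observed.

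**Several bottles.** If one of three bottles is disconnected, the day can score at most 2/3. If another bottle is opened the score is above 0, so c.4 does not register the loss at all.

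**The case against.** The strongest reply is that much of this loss may never occur. The outage message describes trouble retrieving data and promises that donations will follow, which points to delay more than loss. Reconnection calls at study end make most sense if stored openings then upload. Bottles are checked before follow-up and data quality is watched in real time. On the protocol's data path (bottle, phone, Pillsy portal) REDCap carries no time stamps, so a REDCap outage need not lose any. The interior-gap examples require a bottle that reconnects while its gap stays lost, and the documents do not say how common that is. The SAP also supplies partial tools: c.4 yields a flag and a date, and item b.6 yields all daily values, so runs of zeros can be inspected. The days dropped by c.4 remain in the primary aggregation.

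All of this stands, and it limits the expected size. None of it says how to score a day that stays lost, and neither c.4 nor b.6 can separate the causes.

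There is also a fair objection to any repair. The 352 files already exist, so choosing which days become missing is a choice made with data in hand. And for a bottle that never reconnects, lost data and abandonment look the same. Both points shape the fix.

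**Conclusion.** The concern holds in a limited form. On the natural reading, never-recovered days count as missed doses in the primary outcome, and c.4 cannot identify them. The SAP does not say so in words; this follows from its sources, its window and its use of zeros. It is a cheap improvement, held with medium confidence, because the rate of unrecovered days is not in the documents.

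A reader might infer more, and three such readings are not supported:
- That the primary comparison is biased by a known amount or towards a known arm. No loss rates are given, so size and direction are both unknown.
- That the change to the primary outcome below would remove the 0.6, 1.9 or 4.4 points of unequal loss. Those figures belong mainly to disconnection, which stays at 0 in the primary analysis. They show what the sensitivity analysis and the counts by arm could reveal.
- That every outage or disconnection loses data. Only days that remain unrecovered matter.

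The part that the primary analysis can correct is small: about 0.7 points on a between-arm difference for an assumed, never-recovered 7-day outage.

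**What to change.** 1. **Primary outcome.** Set adh_daily to missing, not 0, on Pillsy-side outage days that study records confirm as never recovered, for all affected patients in every arm, and average over the remaining days. Do this before arm is unblinded to the analyst. The SAP's REDCap dataset carries the arm variable, so it should be withheld for this step. Judge recovery by the event times (the SAP works with "Time stamps (eventTime) within 3 hours of each other") across all files and not by file date, because late-synced openings may sit in later files. Days with no event from any patient are only candidates to check.
2. **Disconnection.** State that disconnected days stay 0 in the primary analysis. Add one sensitivity analysis that sets never-recovered disconnected days to missing, applied per bottle and reweighted over the connected medications, with the >30-day censoring based on connection status instead of adh_daily = 0. Report bottles that never reconnect as a separate category.
3. **Reporting.** Give outage days and unrecovered disconnected days by arm beside Table 2.

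The cost is SAP wording, one check of outage records, and some data work to derive connection status. The SAP describes no daily record of it, but the disconnection texts and calls must have relied on one. The downside is that, in the sensitivity analysis, patients who abandoned both bottle and drug may look more adherent than they were. That is why zero-scoring of disconnected days stays primary.
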